**Table 14.2-10 Treatment Interval Summary (Based on Interval Decision)**

Full Analysis Set and Per-Protocol Set

| Statistic | Intensive
(N=X) | Relaxed
(N=X) | Total
(N=X) |
|-----------|--------------------|------------------|----------------|
| n         | x                  | x                | x              |
| Mean      | x.x                | x.x              | x.x            |
| Median    | x.x                | x.x              | x.x            |
| SD        | x.x                | x.x              | x.x            |
| Minimum   | x                  | x                | x              |
| Maximum   | x                  | x                | x              |

SD: Standard Deviation

Average treatment interval for each group - need to average it out for patient then average out for the treatment arm

**Table 14.2-11 Treatment Interval Summary (Based on Actual Intervals between Visits)**

Full Analysis Set and Per-Protocol Set

| Statistic | Intensive
(N=X) | Relaxed
(N=X) | Total
(N=X) |
|-----------|--------------------|------------------|----------------|
| n         | x                  | x                | x              |
| Mean      | x.x                | x.x              | x.x            |
| Median    | x.x                | x.x              | x.x            |
| SD        | x.x                | x.x              | x.x            |
| Minimum   | x                  | x                | x              |
| Maximum   | x                  | x                | x              |

SD: Standard Deviation

Average treatment interval for each group - need to average it out for patient then average out for the treatment arm

**Table 14.2-12 Treatment Interval Visit Summary (Based on Interval Decision)**

Full Analysis Set

| Visit         | Interval | Intensive
(N=x) | Relaxed
(N=x) | Total
(N=x) |
|---------------|----------|--------------------|------------------|----------------|
| Week 4        | 4 Weeks  | x (xx.x%)          | x (xx.x%)        | x (xx.x%)      |
| Week 8        | 4 Weeks  | x (xx.x%)          | x (xx.x%)        | x (xx.x%)      |
| Week 12       | 4 Weeks  | x (xx.x%)          | x (xx.x%)        | x (xx.x%)      |
|               | 6 Weeks  | x (xx.x%)          | x (xx.x%)        | x (xx.x%)      |
|               | 8 Weeks  | x (xx.x%)          | x (xx.x%)        | x (xx.x%)      |
|               | 10 Weeks | x (xx.x%)          | x (xx.x%)        | x (xx.x%)      |
|               | 12 Weeks | x (xx.x%)          | x (xx.x%)        | x (xx.x%)      |
| Week n | 4 Weeks  | x (xx.x%)          | x (xx.x%)        | x (xx.x%)      |
|               | 6 Weeks  | x (xx.x%)          | x (xx.x%)        | x (xx.x%)      |
|               | 8 Weeks  | x (xx.x%)          | x (xx.x%)        | x (xx.x%)      |
|               | 10 Weeks | x (xx.x%)          | x (xx.x%)        | x (xx.x%)      |
|               | 12 Weeks | x (xx.x%)          | x (xx.x%)        | x (xx.x%)      |

**Table 14.2-13 Treatment Interval Visit Summary (Based on Actual Intervals between Visits)**

Full Analysis Set

| Visit         | Interval | Intensive
(N=x) | Relaxed
(N=x) | Total
(N=x) |
|---------------|----------|--------------------|------------------|----------------|
| Week 4        | 4 Weeks  | x (xx.x%)          | x (xx.x%)        | x (xx.x%)      |
| Week 8        | 4 Weeks  | x (xx.x%)          | x (xx.x%)        | x (xx.x%)      |
| Week 12       | 4 Weeks  | x (xx.x%)          | x (xx.x%)        | x (xx.x%)      |
|               | 6 Weeks  | x (xx.x%)          | x (xx.x%)        | x (xx.x%)      |
|               | 8 Weeks  | x (xx.x%)          | x (xx.x%)        | x (xx.x%)      |
|               | 10 Weeks | x (xx.x%)          | x (xx.x%)        | x (xx.x%)      |
|               | 12 Weeks | x (xx.x%)          | x (xx.x%)        | x (xx.x%)      |
| Week n | 4 Weeks  | x (xx.x%)          | x (xx.x%)        | x (xx.x%)      |
|               | 6 Weeks  | x (xx.x%)          | x (xx.x%)        | x (xx.x%)      |
|               | 8 Weeks  | x (xx.x%)          | x (xx.x%)        | x (xx.x%)      |
|               | 10 Weeks | x (xx.x%)          | x (xx.x%)        | x (xx.x%)      |
|               | 12 Weeks | x (xx.x%)          | x (xx.x%)        | x (xx.x%)      |

**Table 14.2-14 Breakpoint Set Interval - Summary**

Full Analysis Set

| Visit    | Interval                      | Intensive
(N=x) | Relaxed
(N=x) | Total
(N=x) |
|----------|-------------------------------|--------------------|------------------|----------------|
| Week 52  | 4 Weeks                       | x (x.xx%)          | x (x.xx%)        | x (x.xx%)      |
|          | 6 Weeks                       | x (x.xx%)          | x (x.xx%)        | x (x.xx%)      |
|          | 8 Weeks                       | x (x.xx%)          | x (x.xx%)        | x (x.xx%)      |
|          | 10 Weeks                      | x (x.xx%)          | x (x.xx%)        | x (x.xx%)      |
|          | 12 Weeks                      | x (x.xx%)          | x (x.xx%)        | x (x.xx%)      |
|          | Has not reached
breakpoint | x (x.xx%)          | x (x.xx%)        | x (x.xx%)      |
| Week 104 | 4 Weeks                       | x (x.xx%)          | x (x.xx%)        | x (x.xx%)      |
|          | 6 Weeks                       | x (x.xx%)          | x (x.xx%)        | x (x.xx%)      |
|          | 8 Weeks                       | x (x.xx%)          | x (x.xx%)        | x (x.xx%)      |
|          | 10 Weeks                      | x (x.xx%)          | x (x.xx%)        | x (x.xx%)      |
|          | 12 Weeks                      | x (x.xx%)          | x (x.xx%)        | x (x.xx%)      |
|          | Has not reached
breakpoint | x (x.xx%)          | x (x.xx%)        | x (x.xx%)      |

**Note to Programmer:** Use assigned interval (Interval Decision)

**Table 14.2-15 Post-Breakpoint Maximum Interval - Summary**

Full Analysis Set

| Visit    | Interval                      | Intensive
(N=x) | Relaxed
(N=x) | Total
(N=x) |
|----------|-------------------------------|--------------------|------------------|----------------|
| Week 52  | 4 Weeks                       | x (x.xx%)          | x (x.xx%)        | x (x.xx%)      |
|          | 6 Weeks                       | x (x.xx%)          | x (x.xx%)        | x (x.xx%)      |
|          | 8 Weeks                       | x (x.xx%)          | x (x.xx%)        | x (x.xx%)      |
|          | 10 Weeks                      | x (x.xx%)          | x (x.xx%)        | x (x.xx%)      |
|          | Has not reached
breakpoint | x (x.xx%)          | x (x.xx%)        | x (x.xx%)      |
| Week 104 | 4 Weeks                       | x (x.xx%)          | x (x.xx%)        | x (x.xx%)      |
|          | 6 Weeks                       | x (x.xx%)          | x (x.xx%)        | x (x.xx%)      |
|          | 8 Weeks                       | x (x.xx%)          | x (x.xx%)        | x (x.xx%)      |
|          | 10 Weeks                      | x (x.xx%)          | x (x.xx%)        | x (x.xx%)      |
|          | Has not reached
breakpoint | x (x.xx%)          | x (x.xx%)        | x (x.xx%)      |

**Note to Programmer:** Use assigned interval (Interval Decision)

**Table 14.2-16 Time to Breakpoint - Summary**

Full Analysis Set

|   | Intensive
(N=x) | Relaxed
(N=x) | Total
(N=x) |
|---|--------------------|------------------|----------------|
| Time to Meet Breakpoint Criteria (weeks) |                    |                  |                |
| n   | x                  | x                | x              |
| Mean  | x.x                | x.x              | x.x            |
| Median  | x.x                | x.x              | x.x            |
| SD  | x.x                | x.x              | x.x            |
| Minimum   | x                  | x                | x              |
| Maximum   | x                  | x                | x              |

SD: Standard Deviation

**Table 14.2-17 Time to Breakpoint – Survival Analysis**

Full Analysis Set

|                               | Intensive
(N=x) | Relaxed
(N=x) | Total
(N=x) |
|-------------------------------|--------------------|------------------|----------------|
| Total Subjects         | x                  | x                | X              |
| Event n(%)                    | x (xx.x%)          | x (xx.x%)        | x (xx.x%)      |
| Censored n(%)                 | x (xx.x%)          | x (xx.x%)        | x (xx.x%)      |
| Time to Events (Weeks) |                    |                  |                |
| 25 Percentile (95% CI)        | x (xx,xx)          | x (xx,xx)        | x (xx,xx)      |
| Median (95% CI)               | x (xx,xx)          | x (xx,xx)        | x (xx,xx)      |
| 75 Percentile (95% CI)        | x (xx,xx)          | x (xx,xx)        | x (xx,xx)      |
| Range                         | xx;xx              | xx;xx            | xx;xx          |

**Table 14.2-18 Geographic Atrophy Area – Summary and Change from Baseline (Central Reading Center Data)**

Full Analysis Set

| Visit         | Statistic | Intensive
(N=X) |                                      | Relaxed
(N=X) |                                     | Total
(N=X) |                                     |
|---------------|-----------|--------------------|--------------------------------------|------------------|-------------------------------------|----------------|-------------------------------------|
|               |           | Actual Value       | Absolute
Change from
Baseline* | Actual Value     | Absolute
Change from
Baseline | Actual Value   | Absolute
Change from
Baseline |
| Screening     | n         | x                  | -                                    | x                | -                                   | x              | -                                   |
|               | Mean      | x.x                | -                                    | x.x              | -                                   | x.x            | -                                   |
|               | Median    | x.x                | -                                    | x.x              | -                                   | x.x            | -                                   |
|               | SD        | x.x                | -                                    | x.x              | -                                   | x.x            | -                                   |
|               | Minimum   | x                  | -                                    | x                | -                                   | x              | -                                   |
|               | Maximum   | x                  | -                                    | x                | -                                   | x              | -                                   |
| Baseline*     | n         | x                  | -                                    | x                | -                                   | x              | -                                   |
|               | Mean      | x.x                | -                                    | x.x              | -                                   | x.x            | -                                   |
|               | Median    | x.x                | -                                    | x.x              | -                                   | x.x            | -                                   |
|               | SD        | x.x                | -                                    | x.x              | -                                   | x.x            | -                                   |
|               | Minimum   | x                  | -                                    | x                | -                                   | x              | -                                   |
|               | Maximum   | x                  | -                                    | x                | -                                   | x              | -                                   |
| Week n | .....     |                    |                                      |                  |                                     |                |                                     |

[Continued through to Month 24](#)

\*Baseline: The last available non-missing value collected just prior to the start of treatment in the study eye  
SD: Standard Deviation

**Table 14.2-19 Geographic Atrophy – Categorical Summary**

Full Analysis Set

| Visit     |         | Intensive | Relaxed   | Total     |
|-----------|---------|-----------|-----------|-----------|
| Baseline* | Present | x (xx.x%) | x (xx.x%) | x (xx.x%) |
|           | Absent  | x (xx.x%) | x (xx.x%) | x (xx.x%) |
| Week 4    | Present | x (xx.x%) | x (xx.x%) | x (xx.x%) |
|           | Absent  | x (xx.x%) | x (xx.x%) | x (xx.x%) |
| Week 8    | Present | x (xx.x%) | x (xx.x%) | x (xx.x%) |
|           | Absent  | x (xx.x%) | x (xx.x%) | x (xx.x%) |
| Week n    | Present | x (xx.x%) | x (xx.x%) | x (xx.x%) |
|           | Absent  | x (xx.x%) | x (xx.x%) | x (xx.x%) |

\*Baseline: The last available non-missing value collected just prior to the start of treatment in the study eye  
SD: Standard Deviation

**Table 14.2-20 Geographic Atrophy – Survival Analysis**

Full Analysis Set

|                        | Intensive
(N=x) | Relaxed
(N=x) | Total
(N=x) |
|------------------------|--------------------|------------------|----------------|
| Total Subjects  | x                  | x                | X              |
| Event n(%)             | x (xx.x%)          | x (xx.x%)        | x (xx.x%)      |
| Censored n(%)          | x (xx.x%)          | x (xx.x%)        | x (xx.x%)      |
| Time to Events (Weeks) |                    |                  |                |
| 25 Percentile (95% CI) | x (xx,xx)          | x (xx,xx)        | x (xx,xx)      |
| Median (95% CI)        | x (xx,xx)          | x (xx,xx)        | x (xx,xx)      |
| 75 Percentile (95% CI) | x (xx,xx)          | x (xx,xx)        | x (xx,xx)      |
| Range                  | xx;xx              | xx;xx            | xx;xx          |
|                        | Intensive
(N=x) | Relaxed
(N=x) | Total
(N=x) |
| Total Subjects  | x                  | x                | X              |
| Event n(%)             | x (xx.x%)          | x (xx.x%)        | x (xx.x%)      |
| Censored n(%)          | x (xx.x%)          | x (xx.x%)        | x (xx.x%)      |
| Time to Events (Weeks) |                    |                  |                |
| 25 Percentile (95% CI) | x (xx,xx)          | x (xx,xx)        | x (xx,xx)      |
| Median (95% CI)        | x (xx,xx)          | x (xx,xx)        | x (xx,xx)      |
| 75 Percentile (95% CI) | x (xx,xx)          | x (xx,xx)        | x (xx,xx)      |
| Range                  | xx;xx              | xx;xx            | xx;xx          |

**Table 14.2-21 Geographic Atrophy – Mixed Model Analysis**

Full Analysis Set

|                                    | Mixed Model* |          |        |         | Treatment Effects |                  |
|------------------------------------|--------------|----------|--------|---------|-------------------|------------------|
|                                    | Num d.f.     | Den d.f. | F-stat | p-value | Intensive (N=X)   | Relaxed (N=X)    |
| Treatment Main Effects             | x            | xx       | x.xx   | x.xxxx  |                   |                  |
| Visits                             | x            | xx       | x.xx   | x.xxxx  |                   |                  |
| Baseline Effect                    | x            | xx       | x.xx   | x.xxxx  |                   |                  |
| Class variable                     | x            | xx       | x.xx   | x.xxxx  |                   |                  |
| Class variable                     | x            | xx       | x.xx   | x.xxxx  |                   |                  |
| Least Squares Means         |              |          |        |         |                   |                  |
| Month 2                            |              |          |        |         | x.xx (x.xx)       | x.xx (x.xx)      |
| Month 12                           |              |          |        |         | x.xx (x.xx)       | x.xx (x.xx)      |
| Month 24                           |              |          |        |         | x.xx (x.xx)       | x.xx (x.xx)      |
| Treatment Effect            |              |          |        |         |                   |                  |
| Month 2, Treatment Effect (95%CI)  |              |          |        |         |                   | x.xx (x.xx,x.xx) |
| Month 2, p-value                   |              |          |        |         |                   | x.xxxx           |
| Month 12, Treatment Effect (95%CI) |              |          |        |         |                   | x.xx (x.xx,x.xx) |
| Month 12, p-value                  |              |          |        |         |                   | x.xxxx           |
| Month 24, Treatment Effect (95%CI) |              |          |        |         |                   | x.xx (x.xx,x.xx) |
| Month 24, p-value                  |              |          |        |         |                   | x.xxxx           |

\*Mixed Model: Change from Baseline (Geographic Atrophy Area) = Baseline (Geographic Atrophy Area) + Treatment + Visit (weeks)  
CI: Confidence Interval; SE: Standard Error

**Note to Programmer:** The above table is an example only. Output to be updated to reflect aspects of the final model as appropriate.

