| Month 24, Treatment Effect (95%CI) |                             |          |        |         |                   | x.xx (x.xx,x.xx) |
| Month 24, p-value                  |                             |          |        |         |                   | x.xxxx           |

\*Mixed Model: Change from Baseline (CRT) = Baseline (CRT) + Treatment + Visit (weeks) + Treatment \* Visit + Subject (random effect)  
CI: Confidence Interval; CRT: Central Retinal Thickness; SE: Standard Error

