2.8.2.5 Mixed Modelling

The mixed models to be fitted are detailed in Table 2.8.2.5-1.

Table 2.8.2.5-1 Mixed Models

Model Number	Outcome Variable	Predictor/Covariate		Class Variable		Random Term
		Definite	Optional	Definite	Optional	
MM_1	Change in BCVA from baseline to 2, 12 and 24 months	
 • Treatment • Baseline BCVA • Visit (categorical) • Treatment by Visit Interaction 	
 • Stratification group • Cumulative weeks on treatment 	Treatment Visit Subject		Subject
MM_2	Change in BCVA from baseline to 2, 12 and 24 months	
 • Treatment • Baseline BCVA • Visit (categorical) • Treatment by Visit Interaction 	
 • Injection frequency • Cumulative number of weeks on treatment • Stratification group Baseline: 
 • Age • Lesion size • GA presence • Smoking status • Genotype saliva sample status • Baseline BCVA (<=70/>70) • Baseline IRF • IRF • Baseline SRF • SRF • PED • SRF resolved (y/n) 	Treatment Visit Subject	Stratum Centre	Subject
MM_3	Change in Geographic Atrophy from baseline to 2, 12 and 24 months.	
 • Treatment • Baseline GA area • Visit (categorical) • Treatment by Visit Interaction 	
 • Cumulative number of weeks on treatment Baseline: 
 • Age • BCVA • Injection frequency • Lesion size • GA presence • Smoking status • Genotype saliva sample status • Baseline BCVA (<=70/>70) • Baseline IRF • IRF • Baseline SRF • SRF • PED • SRF resolved (y/n) 	Treatment Visit Subject	Stratum Centre	Subject

Model Number	Outcome Variable	Predictor/Covariate		Class Variable		Random Term
		Definite	Optional	Definite	Optional	
MM_4	Change in CRT from baseline to 2, 12 and 24 months	
 • Treatment • Baseline CRT • Visit (categorical) • Treatment by Visit Interaction 	
 • Injection frequency • Cumulative number of weeks on treatment • Stratification group Baseline: Age 
 • Lesion size • GA presence • Smoking status • Genotype saliva sample status • Baseline BCVA (<=70/>70) • Baseline IRF • IRF • Baseline SRF • SRF • PED • SRF resolved (y/n) 	Treatment Visit Subject	Stratum Centre	Subject

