All results for all patients for will be included for each model, unless otherwise indicated. The repeated nature of the data will be modelled by including subject as random effect. The Kenward-Roger (KR) correction will be used to compute the denominator degrees of freedom to test fixed effects. The least square (LS) mean estimate for intensive retinal fluid treatment group (“intensive”) – relaxed retinal fluid treatment group (“relaxed”) will be obtained for treatment time = 2 months, 12 months and 24 months. These will be obtained with 95% confidence limits.

In regards to primary efficacy, if the upper 2-sided 95% confidence limit for the least square mean for intensive – relaxed mean change in BCVA at 24 months is <5 (the non-inferiority margin) then relaxed will be declared non-inferior to intensive.

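### The model printed for change in GA area (Tables 14.2-21 and 14.2-22) omits the treatment-by-visit and subject terms of SAP MM_3; programmed as printed, Months 2, 12 and 24 would share one treatment effect

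*Protocol*

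**What the plan says.** In the Protocol document, which holds the table shells, the footnotes of Tables 14.2-21 and 14.2-22 both define the model as "Change from Baseline (Geographic Atrophy Area) = Baseline (Geographic Atrophy Area) + Treatment + Visit (weeks". The formula ends there. The body of each table has separate rows for Months 2, 12 and 24, for example "Month 24, Treatment Effect (95%CI", each with its own p-value. A programmer note under each table says that it is illustrative and must be brought into line with the final model.

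SAP Section 2.8.2.5, Table 2.8.2.5-1, specifies this analysis as MM_3, with outcome "Change in Geographic Atrophy from baseline to 2, 12 and 24 months". Besides treatment, its definite terms are "Baseline GA area • Visit (categorical) • Treatment by Visit Interaction", and its random term is subject. The text after the table states: "The repeated nature of the data will be modelled by including subject as random effect". It adds that the intensive minus relaxed least-squares means "will be obtained for treatment time = 2 months, 12 months and 24 months".

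The corresponding shells for the other outcomes do carry both terms. The CRT footnote (Table 14.2-30) starts in the same form, "Change from Baseline (CRT) = Baseline (CRT) + Treatment + Visit (weeks", but goes on to the treatment-by-visit product and a subject term, "Visit + Subject (random effect". The BCVA footnotes (Tables 14.2-2 and 14.2-3) do the same.

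SAP Table 2.8.2-2 sends the mixed model for GA area to Section 2.8.2.8, which covers logistic regression.

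**The concern.** The shells ask for three month-specific treatment effects from a model that contains only one treatment parameter. They also print a repeated-measures model with no term linking the visits of one eye. Each omission contradicts a term that the SAP specifies for this outcome.

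The GA comparison at Months 12 and 24 is what is at stake. According to the key to the SAP study design figure, both arms receive the same three initial 4-weekly treatments, so little arm difference is expected at Month 2. A model that averages Month 2 with the later visits cannot show a difference that develops afterwards. If the visits are also treated as independent, that averaged effect would carry an interval that is too short.

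**Working it through.** The plan states no figure to reproduce, so the check compares terms first and then works out the consequences.

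**1. Terms side by side.**

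| Term | GA footnotes | MM_3 | BCVA and CRT footnotes |
|---|---|---|---|
| Baseline value | yes | definite | yes |
| Treatment | yes | definite | yes |
| Visit | yes (weeks) | definite, categorical | yes (weeks) |
| Treatment × visit | **no** | definite | yes |
| Subject | **no** | random term | random effect |

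**2. No interaction.** Under baseline + treatment + visit, the arm contrast at any visit is the treatment coefficient β. The Month 2, 12 and 24 effects, intervals and p-values are therefore the same. This is algebra and needs no assumption about the data. Adding a subject effect alone would not change it.

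With complete, balanced data, β estimates the average of the three visit-specific effects:
- Differences of 0, d/2 and d: (0 + d/2 + d)/3 = d/2, half the Month 24 effect.
- Difference growing linearly in time: [(2 + 12 + 24)/3]/24 = 12.67/24 = 0.53 of the Month 24 effect.

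**3. No within-subject covariance (a further condition).** SAP Section 2.8.1 schedules post-baseline GA assessments at week 8, Month 12 and Month 24, so m = 3. With equal variances, complete visits and a common within-eye correlation ρ, the mean of m visits has variance (σ²/m)[1 + (m − 1)ρ]. Independence gives σ²/m. Hence:

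true SE / model SE = √[1 + (m − 1)ρ], and coverage of a nominal 95% interval = 2Φ(1.96/ratio) − 1.

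The documents give no ρ for GA area, so it is assumed:

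| ρ | SE ratio | Coverage |
|---|---|---|
| 0 | 1.00 | 95% |
| 0.5 | √2.0 = 1.41 | 83% |
| 0.7 | √2.4 = 1.55 | 79% |
| 0.9 | √2.8 = 1.67 | 76% |

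With only two visits per eye, the ratio is 1.22 at ρ = 0.5 and 1.38 at ρ = 0.9, with coverage of 89% and about 84%.

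**4. Simulation.** 4,000 trials per scenario, 60 eyes per arm, three visits, total SD 1 (all assumed). Ordinary least squares with the printed terms, under no true difference, rejected in 12%, 17% and 22% of trials at ρ = 0.3, 0.5 and 0.8, and in 5% at ρ = 0. With a true effect growing linearly to 0.50 at Month 24, the printed terms gave about 0.27. The MM_3 terms gave 0.50, with about 95% coverage at every ρ tried.

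**The case against.** The strongest reply is that the SAP already specifies the correct model and the shells tell the programmer to update them, so the error appears only if both are ignored. That lowers the risk, but it does not settle the matter. The same note sits under both BCVA shells, whose footnotes carry both terms, so it does not tell a reader that definite terms are missing from the GA footnotes. The SAP's pointer also fails for this endpoint: Table 2.8.2-2 leads to the logistic regression section rather than to MM_3.

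A second reply is that the GA shells are unfinished templates. They contain placeholder rows for class variables, and the CRT shell likewise has no Treatment*Visit row in its body. This is fair: the missing row is not peculiar to GA. The footnote formula is, because the BCVA and CRT footnotes are complete.

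A third reply concerns independence. A reader might infer that the intervals will certainly be too narrow. The documents do not support that. The tables are titled and labelled as mixed models and have a column for denominator degrees of freedom, so the footnote may list fixed effects only. The standard-error result in step 3 therefore needs two conditions: no within-subject covariance is fitted, and ρ is positive. Positive ρ is to be expected for repeated areas in one eye, but the documents do not state it. This objection stands and makes that part conditional.

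A reader might also infer that GA is the main structural safety signal between the regimens. The documents do not say so. SAP Section 2.8.1 lists GA area among the additional secondary efficacy variables, and the safety parameters in Section 2.9 do not include it.

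**Conclusion.** The shells contradict the SAP, and the point stands as a SHOULD item on an additional secondary endpoint. The primary BCVA non-inferiority test is unaffected.

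The certain part is that a program written to the printed formula would return one effect, one interval and one p-value in all three month rows. The size of the dilution depends on how the difference develops. It is about half the Month 24 effect under either assumed pattern, with complete and balanced data.

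The conditional part is the precision. The figures of 1.41 to 1.67 for the standard error and 83% to 76% for coverage apply only if no within-subject covariance is fitted, and they rest on three visits per eye, equal variances and ρ between 0.5 and 0.9. They do not show that the trial's GA intervals will be wrong.

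**What to change.** Replace the footnotes of Tables 14.2-21 and 14.2-22 with MM_3: baseline GA area + treatment + visit (categorical) + treatment*visit + subject (random effect). Add a Treatment*Visit row to both tables, and take the month-specific effects from the model with the interaction. In SAP Table 2.8.2-2, change the cross-reference for the GA-area mixed model from Section 2.8.2.8 to Section 2.8.2.5.

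The cost is shell wording, one cross-reference and the matching program code. No new data or modelling decision is needed, since this restores the model already specified.

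One related matter remains open. SAP Sections 2.8.1 and 2.8.2 also describe GA area change measured from the visit at which GA first appeared, whereas MM_3 and the shells use change from baseline. Copying MM_3 into the footnotes does not resolve that difference, so the SAP should state which outcome these tables report.
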